11.4 Discontinuation of the study

Novartis reserves the right to discontinue this study under the conditions specified in the clinical study agreement. Specific conditions for terminating the study are outlined in Section 4.4.

11.5 Publication of study protocol and results

Novartis is committed to following high ethical standards for reporting study results for its innovative medicine, including the timely communication and publication of clinical trial results, whatever their outcome. Novartis assures that the key design elements of this protocol will be posted on the publicly accessible database, e.g. www.clinicaltrials.gov before study start. In addition, results of interventional clinical trials in adult patients are posted on www.novartisclinicaltrials.com, a publicly accessible database of clinical study results within 1 year of study completion (i.e., LPLV), those for interventional clinical trials involving pediatric patients within 6 months of study completion.

Novartis follows the ICMJE authorship guidelines (www.icmje.org) and other specific guidelines of the journal or congress to which the publication will be submitted

Authors will not receive remuneration for their writing of a publication, either directly from Novartis or through the professional medical writing agency. Author(s) may be requested to present poster or oral presentation at scientific congress; however, there will be no honorarium provided for such presentations.

As part of its commitment to full transparency in publications, Novartis supports the full disclosure of all funding sources for the study and publications, as well as any actual and potential conflicts of interest of financial and non-financial nature by all authors, including medical writing/editorial support, if applicable.

For the Novartis Guidelines for the Publication of Results from Novartis-sponsored Research, please refer to www.novartis.com.

11.6 Study documentation, record keeping and retention of documents

Each participating site will maintain appropriate medical and research records for this trial, in compliance with Section 4.9 of the ICH E6 GCP, and regulatory and institutional requirements for the protection of confidentiality of subjects. As part of participating in a Novartis-sponsored study, each site will permit authorized representatives of the sponsor(s) and regulatory agencies to examine (and when required by applicable law, to copy) clinical records for the purposes of quality assurance reviews, audits and evaluation of the study safety and progress.

Source data are call information, original records of clinical findings, observations, or other activities in a clinical trial necessary for the reconstruction and evaluation of the trial. Examples of these original documents and data records include, but are not limited to, hospital records, clinical and office charts, laboratory notes, memoranda, subjects' diaries or evaluation checklists, pharmacy dispensing records, recorded data from automated instruments, copies or transcriptions certified after verification as being accurate and complete, microfiches, photographic negatives, microfilm or magnetic media, x-rays, and subject files and records kept at the pharmacy, at the laboratories, and medico-technical departments involved in the clinical trial.

Data collection is the responsibility of the clinical trial staff at the site under the supervision of the site Principal Investigator. The study case report form (CRF) is the primary data collection instrument for the study. The investigator should ensure the accuracy, completeness, legibility, and timeliness of the data reported in the CRFs and all other required reports. Data reported on the CRF, that are derived from source documents, should be consistent with the source documents or the discrepancies should be explained. All data requested on the CRF must be recorded. Any missing data must be explained. Any change or correction to a paper CRF should be dated, initialed, and explained (if necessary) and should not obscure the original entry. For electronic CRFs an audit trail will be maintained by the system. The investigator should retain records of the changes and corrections to paper CRFs.

The investigator/institution should maintain the trial documents as specified in Essential Documents for the Conduct of a Clinical Trial (ICH E6 Section 8) and as required by applicable regulations and/or guidelines. The investigator/institution should take measures to prevent accidental or premature destruction of these documents.

Essential documents (written and electronic) should be retained for a period of not less than fifteen (15) years from the completion of the Clinical Trial unless Sponsor provides written permission to dispose of them or, requires their retention for an additional period of time because of applicable laws, regulations and/or guidelines.

11.7 Confidentiality of study documents and patient records

The investigator must ensure anonymity of the patients; patients must not be identified by names in any documents submitted to Novartis. Signed informed consent forms and patient enrollment log must be kept strictly confidential to enable patient identification at the site.

11.8 Audits and inspections

Source data/documents must be available to inspections by Novartis or designee or Health Authorities.

11.9 Financial disclosures

Financial disclosures should be provided by study personnel who are directly involved in the treatment or evaluation of patients at the site - prior to study start.

12 Protocol adherence

Investigators ascertain they will apply due diligence to avoid protocol deviations. Under no circumstances should the investigator contact Novartis or its agents, if any, monitoring the study to request approval of a protocol deviation, as no authorized deviations are permitted. If the investigator feels a protocol deviation would improve the conduct of the study this must be considered a protocol amendment, and unless such an amendment is agreed upon by Novartis and approved by the IRB/IEC/REB it cannot be implemented. All significant protocol deviations will be recorded and reported in the CSR.

This document supports one final analysis for safety and efficacy. Final analysis will be reported in a final CSR to support the license renewal submission and fulfill a post approval commitment (PAC).

The current analysis plan is based on the final protocol (Version 02) and original mock CRF draft ver0.3.

1.1 Study design

This is an open label, single arm, multi-center phase IV study of treatment with one daily oral dose of 10 mg everolimus (Afinitor®) in 40 patients with renal angiomyolipoma associated with TSC.

There are three separate phases in this study: a “Screening phase”, an “Open-label treatment phase”, and a “Treatment discontinuation follow-up phase” for patients who discontinue study drug for other reasons than disease progression.

A final analysis will be performed after all patients have completed Week 48 (or discontinued earlier but were followed up for efficacy up to Week 48) and their safety follow-up visit.

1.2 Study objectives and endpoints

Objectives and related endpoints are described in [Table 1.2-1](#) below.

Table 1.2-1 Objectives and related endpoints

Objective	Endpoint	Analysis
Primary		
To evaluate the safety of Afinitor® in Chinese adults with TSC-AML not requiring immediate surgery.	
 • Incidence of adverse events, lab abnormalities 	Refer to Section 2.8
Secondary		
To evaluate the efficacy of Afinitor® in Chinese adults with TSC-renal AML not requiring immediate surgery.	
 • AML response 	Refer to Section 2.7.1
Other Secondary		
To further evaluate the efficacy of Afinitor® in Chinese adults with TSC-renal AML not requiring immediate surgery.	
 • AML progression • Renal function change from screening 	Refer to Section 2.7.1
Exploratory		
None		

2 Statistical methods

2.1 Data analysis general information

Novartis will be performing the final analysis.

SAS version 9.4 or higher will be used to conduct the analysis.

Categorical data will be presented as frequencies and percentages. For continuous data, the number of patients with assessable data, mean, standard deviation, median, minimum, maximum, lower quartile, and upper quartile will be presented. For time-to-event analyses, the number of patients at risk, the number and percentage of patients at risk with the event, the number and percentage of patients censored with the reason for censoring, Kaplan-Meier survival estimates with 95% CIs every 3 months, the median survival estimate and the 25th and 75th percentiles survival estimates with their 95% CI will be presented.

2.1.1 General definitions

2.1.1.1 Study drug and study treatment

The investigational drug used in the course of this study will be relabeled local commercial Afinitor® (everolimus).

Definition of terms: Study treatment = RAD001 = Afinitor® = everolimus.

2.1.1.2 Date of first administration of study treatment

The date of first administration of RAD001 is defined as the first date when a non-zero dose of RAD001 was administered, as per the Study Treatment CRF. For the sake of simplicity, the date of first administration of study drug will also be referred to as the start of study drug.

2.1.1.3 Date of last administration of study treatment

The date of last administration of RAD001 is defined as the last date when a non-zero dose of RAD001 was administered and recorded on the Study Treatment CRF.

2.1.1.4 Study day

The study day *for safety assessments* (e.g., adverse event (AE) onset date, laboratory abnormality occurrence, vital sign measurement, dose interruption) will be calculated using the start date of study treatment as the origin.

Safety assessments that occur on or after the start date of study treatment will have study day calculated as

$$(\text{date of safety assessment}) - (\text{start date of study treatment}) + 1.$$

Safety assessments that occur before the start date of study treatment will have study day calculated as

$$(\text{date of safety assessment}) - (\text{start date of study treatment}).$$

Then study day 1 will be the first day of study treatment and study day -1 will be the day before the first day of study treatment.

The study day *for all other, i.e., non-safety assessments* (e.g., Magnetic Resonance Imaging [MRI] assessment, angiomyolipoma progression, angiomyolipoma response, World Health Organization [WHO] performance status) will be calculated as same as safety assessments.

Study day will be displayed in the data listings.

2.1.1.5 Baseline

The baseline will be defined when appropriate as the last available assessment on or before the start date of RAD001.

2.1.1.6 On-treatment assessment/event

Adverse event summaries will present only on-treatment assessments, where on-treatment means that the AE started in the following time interval in the open-label period (including the lower and upper limits):

<date of first administration of open-label RAD001; date of last administration of open-label RAD001 + 30 days>.

Other safety summaries will present baseline and on-treatment assessments, where on-treatment means that the assessment occurred in the following time interval in the open-label period (including the lower and upper limits):

<date of first administration of open-label RAD001 + 1; date of last administration of open-label RAD001 + 30 days>.

2.1.1.7 Time windows

In order to summarize data over time, the following data types will be time slotted using time windows.

CT/MRI assessments for efficacy

CT/MRI assessments for efficacy will be performed at screening/baseline, and at 12, 24 and 48 weeks after the start of study treatment, and at the End of Treatment visit.

- The baseline time window is defined as being any time on or before the start of study treatment.
- The first on-study time window is from study day 2, i.e., the day after the start of study treatment, until study day 126 (i.e., week 18). The upper limit of this time window is midway between the first and second planned post baseline CT/MRI assessments, i.e., at weeks 12 and 24.
- The second on-study time window is from study day 127 until study day 252 (i.e., week 36). The lower limit of this time window is midway between the first and second planned post baseline CT/MRI assessments, i.e., at weeks 12 and 24, and the upper limit is midway between the second and third planned CT/MRI assessments, i.e., at weeks 24 and 48.

- The third on-study time window is from study day 253 until study day 343 (i.e., week 48 + 7 days). The lower limit of this time window is midway between the second and third planned post baseline CT/MRI assessments, i.e., at weeks 24 and 48, and the upper limit is day between the third assessment and its 7 day window, i.e., at weeks 48 and weeks 48 + 7 days.

Table 2.1-1 summarizes the time windows for CT/MRI assessments for efficacy.

Table 2.1-1 Time windows for CT/MRI assessments for efficacy

Time Window	Planned Visit Timing	Time Window Definition
Baseline	On or before Study Day 1	≤ Study Day 1
Week 12	Study Day 84	Study Days 2 – 126 (Baseline to Week 18)
Week 24	Study Day 168	Study Days 127 – 252 (Week 18 to Week 36)
Week 48	Study Day 336	Study Days 253 – 343 (Week 36 to Week 48 + 7 days)

Study Day 1 = Start date of study treatment

If more than one assessment is done within the Baseline time window, the assessment closest to study day 1 (i.e., the start of study treatment) will be used; if two or more assessments are equidistant from study day 1, then the mean value will be used. For all other time windows, the assessment closest to the planned assessment date will be used; if two or more assessments are equidistant from the planned date, then the mean value will be used.

Pulmonary function tests

Pulmonary function tests (PFT) will be performed on sporadic LAM and LAM patients at screening/baseline, and at 12, 24 and 48 weeks after the start of study treatment, and at the End of Treatment visit.

Table 2.1-2 summarizes the time windows for pulmonary function tests.

Table 2.1-2 Time windows for pulmonary function tests

Time Window	Planned Visit Timing	Time Window Definition
Baseline	On or before Study Day 1	≤ Study Day 1
Week 12	Study Day 84	Study Days 2 – 126 (Baseline to Week 18)
Week 24	Study Day 168	Study Days 127 – 252 (Week 18 to Week 36)
Week 48	Study Day 336	Study Days 253 – 343 (Week 36 to Week 48 + 7 days)

Study Day 1 = Start date of study treatment

If more than one assessment is done within the Baseline time window, the assessment closest to study day 1 (i.e., the start of study treatment) will be used; if two or more assessments are equidistant from study day 1, then the mean value will be used. For all other time windows, the assessment closest to the planned assessment date will be used; if two or more assessments are equidistant from the planned date, then the mean value will be used.

WHO performance status

WHO performance status will be collected at screening/baseline, on the start date of study treatment, at 4, 12, 24 and 48 weeks, and at the End of Treatment visit.

Table 2.1-3 summarizes the time windows for WHO performance status.

Table 2.1-3 Time windows for WHO performance status

Time Window	Planned Visit Timing	Time Window Definition
Baseline	On or before Study Day 1	≤ Study Day 1
Week 4	Study Day 28	Study Days 2 – 42 (Baseline to Week 6)
Week 12	Study Day 84	Study Days 43 – 126 (Week 6 to Week 18)
Week 24	Study Day 168	Study Days 127 – 252 (Week 18 to Week 36)
Week 48	Study Day 336	Study Days 253 – 343 (Week 36 to Week 48 + 7 days)

Study Day 1 = Start date of study treatment

If more than one assessment is done within the Baseline time window, the assessment closest to study day 1 (i.e., the start of study treatment) will be used; if two or more assessments are equidistant from study day 1, then the mean value will be used. For all other time windows, the assessment closest to the planned assessment date will be used; if two or more assessments are equidistant from the planned date, then the mean value will be used.

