7.1.3 Treatment period

Patients will receive the first dose of study drug on Day 1 and continue to be treated per protocol until documentation of angiomyolipoma progression, unacceptable toxicity, pregnancy, withdrawal of consent or investigator decision to stop the study. However, study treatment may prematurely be discontinued for other reasons as well; please refer to [Section 7.1.4](#). The maximum treatment duration is 48 weeks. Patients will visit the investigator site 4, 12, 24, and 48 weeks from Day 1 (± 7 days) and be followed as per the schedule of assessments. At these visits sufficient study drug will be dispensed to the patients to last until the next scheduled visit and unused drug will be returned to the site. Compliance will be assessed by the investigator and/or study personnel at each visit using pill counts and information provided by the patient or caregiver. This information should be captured in the source document at each visit.

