contrast. CT without contrast medium is not a recommended modality but accepted if none of the other modalities can be performed.

For instructions regarding screening assessments of angiomyolipoma lesions, please refer to [Section 7.1.2.3](#).

- **Brain**
A brain scan should be completed at screening to identify if any SEGA lesions are present. Preferred modality: MRI with contrast medium.
If MRI contrast medium is not tolerated a contrast enhanced CT or MRI/CT without contrast are acceptable.
- **Lung (thorax)**
A thorax scan at screening is only required if clinically indicated for patients with LAM. Preferred modality: CT with contrast medium.
If a patient is known to have a contraindication to intravenous CT contrast media or develops a contraindication during the trial, a non-contrast CT can be performed. MRI is not recommended due to respiratory artifacts, however if CT is not feasible per local regulations, MRI can be performed instead.
- **Skin lesions**
If skin lesions are present at screening, digital color photographs should be taken using a high resolution digital camera (≥ 3 megapixels) in clear focus, including a caliper, scale or ruler, in such a way that the size of the lesion(s) can be determined from the photograph.

Imaging assessments during treatment and treatment discontinuation follow-up phase

Imaging assessments as described in [Table 7-3](#) should be performed using the same imaging modality used at screening, irrespective of study treatment interruption or actual dosing (see [Table 7-1](#)). Imaging assessments for response evaluation will be performed 12, 24, and 48 weeks after start of treatment and at End of Treatment. The End of Treatment assessments can be omitted if the most recent assessment was done less than 8 weeks ago. Imaging assessments should be scheduled using the treatment start date as the reference date, and should be respected regardless of whether treatment with study treatment is temporarily withheld or unscheduled assessments performed.

Table 7-3 Imaging collection plan

Procedure (see below for the preferred imaging modalities, requirements to use contrast medium)	Screening	"Open-Label treatment" phase and "Treatment Discontinuation Follow-up" phase where applicable
Abdomen and pelvis CT or MRI (pelvis only if required due to kidney size)	Mandated	Mandated at 12, 24, 48 weeks and at EOT

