Kaplan-Meier estimates up to 48 weeks can be interpreted as fully valid. However, beyond that point where censoring was occurring due to treatment completion, the estimates are extremely undependable due to the high variability introduced by the small number of patients remaining in the risk set. In particular, the progression event in the patient with the longest TTAP causes the KM curve to drop to zero which is not meaningful; it is just an artifact of the KM calculation. In order to perform a somewhat interpretable analysis at this late timepoint, a revised analysis was introduced in which all patient outcomes (censoring or event) occurring after the maximum treatment duration will be considered to have occurred at the same timepoint. Specifically:

For TTAP exceeding the maximum treatment duration of 48 weeks + 7day window (11.268 months), the TTAP will be reassigned to 11.268 months. Then the Kaplan-Meier curve will be re-computed using this revised time definition.

It should be kept in mind that the KM event rate at the end of the study using this approach is very likely still over-estimated: the KM curve still drops noticeably because there were only 9 patients in the risk set beyond the end of treatment. Nevertheless, there was no signal in the data of a likely large increase in that narrow timeframe. Although this revised estimate ignores an event when it actually occurred, it does allow incorporation of that single late event in a more reasonable manner than using the raw data. Therefore, it is reasonable to say that the estimates up to the end of the Week 48 assessment window can be interpreted as fully valid.

Time to angiomyolipoma response

Time to angiomyolipoma response is defined as the time from the start date of everolimus until the date of the first documented angiomyolipoma response, where angiomyolipoma response is as defined as above. Time to angiomyolipoma response applies only to patients who achieve an angiomyolipoma response, i.e., patients in the analysis will have known times to angiomyolipoma response and there will be no censored times.

Time to angiomyolipoma response is calculated in months as

$$(\text{Date of first AML response} - \text{Start date of everolimus} + 1) \times 12 \div 365.25.$$

The median time to angiomyolipoma response will be presented along with a 95% confidence interval, and the proportions of angiomyolipoma responders who respond by 3, 6, and 12 months will be provided.

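### The SAP's Week 48 window ends one study day before the protocol's visit window, so an on-time Day 344 assessment has no Week 48 slot

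*SAP*

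**What the plan says.** SAP 2.1.1.4 computes study day, on or after the start of treatment, as the date minus the start date plus one: "Then study day 1 will be the first day of study treatment". Study day for efficacy assessments "will be calculated as same as safety assessments".

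Both documents time visits in weeks from the start of treatment:
- SAP 2.1.1.7 places CT/MRI "at 12, 24 and 48 weeks after the start of study treatment".
- Protocol 7.1.3 says "Patients will visit the investigator site 4, 12, 24, and 48 weeks from Day 1", and protocol 7.1 allows 7 days either side.
- Protocol 7.2.1 adds that "Imaging assessments should be scheduled using the treatment start date as the reference date".

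SAP 2.1.1.7 then sets planned days of 84, 168 and 336 for CT/MRI and lung function (Tables 2.1-1 and 2.1-2). Table 2.1-3 uses the same days plus Day 28 for WHO performance status. On the upper end it says "The third on-study time window is from study day 253 until study day 343 (i.e., week 48 + 7 days". None of the tables has a window after Day 343.

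SAP 2.7.1 uses a related limit for TTAP: "For TTAP exceeding the maximum treatment duration of 48 weeks + 7day window (11.268 months", the time is reset to that value. It reports 9 patients beyond the limit, one of whom progressed and had the longest TTAP.

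**The concern.** The day tables and the study-day formula do not agree. If the first dose is Day 1, a visit exactly *n* weeks later is Study Day 7*n* + 1, not 7*n*. Day 343 is therefore 48 weeks + 6 days, although the SAP labels it 48 weeks + 7 days.

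A patient seen on the last day the protocol allows is on time but has no Week 48 slot. Unless that patient has another assessment between Days 253 and 343, the Week 48 value is missing from the by-visit summaries of target lesion volume, lung function or performance status. With 40 patients, each value lost from an all-patient summary is 1/40 = 2.5% of the sample.

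The TTAP cap rests on the same Day 343, so the description of patients as beyond the treatment period plus window may include someone who was seen on time.

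**Working it through.** **Inputs.** Study day = date − start + 1 (SAP 2.1.1.4). Visits at 4, 12, 24 and 48 weeks from Day 1, ±7 days (protocol 7.1 and 7.1.3). TTAP in months = (date − start + 1) × 12/365.25 (SAP 2.7.1).

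**1. Reproducing the SAP's figures.** Week *n* = Day 7*n* gives 28, 84, 168 and 336. The CT/MRI boundaries are (84 + 168)/2 = 126 and (168 + 336)/2 = 252. The upper limit is 48 × 7 + 7 = 343. The cap is 343 × 12/365.25 = 11.26899 months, which rounds to 11.269; the printed 11.268 is that value truncated.

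**2. Applying the SAP's own formula.**

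| Time after start | Days elapsed | Study day by formula | SAP table |
|---|---|---|---|
| 4 weeks | 28 | 29 | 28 |
| 12 weeks | 84 | 85 | 84 |
| 24 weeks | 168 | 169 | 168 |
| 48 weeks | 336 | 337 | 336 |
| 48 weeks + 7 days | 343 | 344 | 343 |

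The midpoints become (85 + 169)/2 = 127 and (169 + 337)/2 = 253.

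**3. What falls outside.** The protocol's Week 48 visit runs from Day 48 × 7 − 7 + 1 = 330 to Day 344, which is 15 days. The SAP window (Days 253 to 343) covers 14 of them. Day 344 has no slot.

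**4. The TTAP cap.** Day 344 is 344 × 12/365.25 = 11.302 months, or 0.034 above the printed cap. A Day 343 outcome (11.26899) also exceeds the printed 11.268, although Day 343 lies inside the SAP's own window.

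**5. Effect on the Kaplan-Meier estimate.** The SAP has 9 patients in the last risk set and one event, so the last step is a relative drop of 1/9.
- *Truncation.* A Day 343 outcome ties with the capped outcomes under either 11.268 or 11.26899. The estimate does not change.
- *Patients censored on Day 344.* With the cap at Day 344 they still tie with the event, so the risk set stays at 9. They no longer count as exceeding the limit. If 4 of the 8 censored patients were on Day 344, that count would fall from 9 to 5.
- *Patients censored on Day 343.* With the cap at Day 344 they leave the last risk set. If *k* of the 8 are on Day 343, the drop becomes 1/(9 − *k*); for *k* = 1 it is 1/8.
- *Illustration.* Assume the other two progressions came before any censoring among 40 patients, so the estimate before the last step is 38/40 = 0.95. The final estimate is then 0.95 × 8/9 = 0.844 for *k* = 0 and 0.95 × 5/6 = 0.792 for *k* = 3. The actual dates are not given.

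**The case against.** The SAP is internally regular. Week *n* = Study Day 7*n* is used for every planned day in all three tables, and each planned day and limit is printed, so a programmer faces no ambiguity. That stands, but it does not create a slot for a compliant Day 344 visit.

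A reader might infer more than the documents support in four ways.

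- *That the 11.268-month cap is simply wrong.* SAP 2.7.1 ties the cap to maximum treatment duration plus 7 days. SAP 2.4.1 counts duration inclusively, so 48 weeks of dosing is Days 1 to 336, and 336 + 7 = 343. Apart from the third decimal, the cap follows from that. It is one day short only when it is meant to mark the end of the protocol visit window.
- *That the revised Kaplan-Meier rule depends on the count of 9.* The SAP says the rule was introduced because the longest TTAP was an event and took the curve to zero. That would hold with a smaller count.
- *That several patients must be affected.* An even spread of 40 visits over 15 days would put 40/15 = 2.7 on Day 344. Nothing in the documents supports an even spread or 40 Week 48 assessments: kidney scans are scheduled only until progression, and lung tests are for LAM patients only.
- *That the main results move.* The windows serve summaries over time. The response and progression rates and TTAP are not defined through them, and adverse events are counted up to 30 days after the last dose.

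**Conclusion.** The inconsistency is real and minor. By the SAP's own study-day formula the protocol's Week 48 window ends at Day 344. The SAP tables end at Day 343, so an on-time Day 344 assessment is left out of the Week 48 descriptive summaries. This is one permitted day in 15. The number of patients affected is unknown without visit dates and may be zero.

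The conclusion assumes that weeks are counted from the date of first dose, as both documents say. The response rate, the progression rate and the primary safety endpoint are unaffected. For TTAP the issue is consistency between the cap and the visit window: the cap's time label changes, the count of 9 may change, and the last Kaplan-Meier step changes only if someone was censored exactly on Day 343.

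**What to change.** 1. End the Week 48 window at Study Day 344 in Tables 2.1-1, 2.1-2 and 2.1-3.
2. State one convention. Either use planned Days 29 (performance status only), 85, 169 and 337 and move the boundaries by one day, or say that Week *n* means Study Day 7*n* and still slot Day 344 into Week 48. When editing Table 2.1-3, also check its Week 4 to Week 12 boundary: Day 42 is labelled Week 6, whereas the midpoint of Days 28 and 84 is 56.
3. For consistency, set the TTAP cap at Study Day 344 (11.302 months) and apply it in days, so that rounding of months cannot decide who exceeds it.
4. Recheck the count of 9 patients and report how many, if any, fall on Days 343 and 344.

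The cost is a few constants in the SAP and programs, plus a rerun of the by-visit tables and the TTAP curve; no new data are needed. There is one downside. Any patient censored exactly on Day 343 leaves the last risk set under the later cap, which enlarges a final step that the SAP already regards as probably overstated. If there is no such patient, only the time label and possibly the count change.
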